1.3.1.2.2 T-Guard Single-arm, Phase 1/2 Clinical trial in second-line SR-aGVHD Patients

Following the promising results of T-Guard for the indication SR-aGVHD in the investigator-initiated dose escalation study, a Phase 1/2 study XEN/TG-001 was conducted (Groth, van Groningen et al. 2018). The study was designed to evaluate the safety and efficacy of T-Guard in treating SR-aGVHD patients who were refractory to first-line therapy. In total 20 patients were treated with T-Guard with a dose of 4 mg/m² every other day x 4 doses. All patients had grade II to IV SR-aGVHD. Seventeen of these patients (85%) had grade III-IV SR-aGVHD, and all 20 patients had visceral involvement; 18 with GI (90%) and 5 with liver (25%) involvement. Sixteen patients (80%) had 2 or more organs involved. A validated two biomarker algorithm classified the majority of patients (11/20) as high-risk.

The Day 28 ORR (primary endpoint), defined as having a CR or PR without the need for initiation of other treatments due to insufficient response, was 60%. Day 28 CR was 50% and PR 10%. The Day 180 OS was 60%. The outcomes achieved were very favorable compared with the historical standard of care (SoC) data at the participating centers (Day 28 CR less than 20% and Day 180 OS 29%).

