
Myalgia and serum CK-elevation:

There is an association of myositis with Ricin-based toxicity. Therefore, participants should be monitored for signs of myositis. If participants experience muscle pain, then a serum CK should be performed. The next dosage of T-Guard should be withheld in case of a CK elevation greater than 5 times ULN. Dosing can resume if the CK decreases to less than or equal to 5 ULN and symptoms of myositis has improved to Grade 2 or less by CTCAE v.5. Dosing can proceed at the investigator's discretion if deemed in the best interest of the participant.

Other toxicities:

Participants with another non-hematologic grade 3 or higher toxicity which is not attributable to an expected post-transplant event may have their study drug held at the attending physician's discretion. Expected post-transplant events include steroid-related toxicity and chemotherapy toxicity. T-Guard should be restarted after recovery of related toxicities to grade 2 or lower or identification of an alternative cause for these toxicities.

Infection:

Participants with severe infections resulting in hemodynamic instability requiring use of vasopressor medication may have study drug held at the discretion of the treating physician.

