2.5.2.5 Dose Modifications for Ruxolitinib

Ruxolitinib dose will be adjusted for toxicity. Dose modification guidelines are based on the occurrence and intensity of specific adverse events that are suspected to be drug related. No dose reduction of ruxolitinib starting dose is required for concomitant strong CYP3A4 inhibitors/dual inhibitors. The most relevant information has been provided in [Table 2-1](#). [Table 2-2](#) provides dose reduction steps for ruxolitinib dosing.

Table 2-1: Required Treatment Modification Guidelines for Ruxolitinib-related Toxicities

Grade by NCI CTCAE# ¹	Action ²
Neutrophil count decreased	Grade 3: Decrease 1 dose level (see Table 2-2), monitor ANC daily until resolved to \leq Grade 2, then resume initial dose level Grade 4: Hold dose, monitor ANC daily until resolved until \leq Grade 3, then resume at next lower dose level. If resolves to \leq Grade 2, can resume initial dose level. If not resolved in \leq 14 days while holding, drug must be discontinued.
Febrile neutropenia	Grade 3: Hold dose until resolved, then restart at next lower dose level.
Thrombocytopenia	Grade 4: (plt <20,000 – 15,000/mm ³): Decrease 1 dose level until resolved to \geq 20,000/mm ³ . If resolved in \leq 7 days, then resume initial dose level. If resolved in > 7 days, then maintain the decreased dose. Grade 4: (plt <15,000/mm ³): Hold dose until resolved to \geq 20,000/mm ³ . If resolved to \leq Grade 3, can resume initial dose level. If not resolved in \leq 14 days while holding, drug must be discontinued.
Serum creatinine	Grade 2: Decrease 1 dose level until resolved to \leq Grade 1 or baseline, then resume initial dose level Grade 3: Hold dose until resolved to \leq Grade 2, then restart at next lower dose level. If resolves to \leq Grade 1 can resume initial dose level. Grade 4: Discontinue ruxolitinib.

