Total bilirubin increased	Grade 3: (> 3.0 – 5.0 x ULN): Decrease 1 dose level until resolved to \leq 3.0 x ULN. Monitor LFTs at least weekly, until resolved to \leq 3.0 x ULN. If resolved \leq 14 days, then resume initial dose level. If resolved in > 14 days, then maintain the decreased dose level. Grade 3: (>5.0 – 10.0 x ULN): Hold dose. Monitor LFTs at least weekly until resolved to \leq 3.0 x ULN. If resolved \leq 14 days, then resume same dose level. If resolved in > 14 days, then restart at the next lower dose level. Grade 4: Hold dose. Monitor LFTs at least weekly until resolved to \leq 3.0 x ULN. If resolved \leq 14 days, then resume at the next lower dose level. If resolved in > 14 days, then drug must be discontinued. LFTs should be monitored at least weekly until total bilirubin has resolved to baseline or stabilized over 4 weeks.

Grade by NCI CTCAE ¹	Action ²
ALT or AST increased	⁴ Grade 2: (for pts with normal baseline value \leq 3.0 x ULN) Maintain the dose level and repeat LFTs as soon as possible, preferably within 48-72 hours from abnormal result awareness. If abnormal lab values are confirmed, decrease dose to the next lower level until resolved to \leq 3.0 x ULN. Continue to monitor LFTs at least weekly until resolved to \leq 3.0 x ULN. If resolved \leq 14 days, then resume initial dose level. If resolved > 14 days, then continue at the decreased dose level.
	⁴ Grade 2: (for pts with baseline value > 3.0 – 5.0 x ULN): Maintain dose level. Monitor LFTs at least weekly until resolved to \leq baseline.
	Grade 3: (>5.0 - 10.0 x ULN): Hold dose. Repeat LFTs as soon as possible, preferably within 48-72 hours from abnormal result awareness. Monitor LFTs at least weekly until resolved to \leq 5.0 x ULN. If resolved \leq 14 days, then resume same dose level. If resolved > 14 days, then continue at the next lower dose level.
	Grade 3: (>10.0 – 20.0 x ULN): Hold dose. Repeat LFTs as soon as possible, preferably within 48-72 hours from abnormal result awareness. Monitor LFTs at least weekly until resolved to \leq 5.0 x ULN then resume at the next lower dose level.

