APPENDIX C: STAGING AND GRADING OF ACUTE GVHD (HARRIS, YOUNG ET AL. 2016)

6

A.C. Harris *et al.* / Biol Blood Marrow Transplant 22 (2016) 4–10

Table 1
GVHD Target Organ Staging

Stage	Skin (Active Erythema Only)	Liver (Bilirubin)	Upper GI	Lower GI (stool output/day)
0	No active (erythematous) GVHD rash	<2 mg/dL	No or intermittent nausea, vomiting, or anorexia	Adult: <500 mL/day or <3 episodes/day Child: <10 mL/kg/day or <4 episodes/day
1	Maculopapular rash <25% BSA	2-3 mg/dL	Persistent nausea, vomiting or anorexia	Adult: 500–999 mL/day or 3–4 episodes/day Child: 10–19.9 mL/kg/day or 4–6 episodes/day
2	Maculopapular rash 25–50% BSA	3.1–6 mg/dL		Adult: 1000–1500 mL/day or 5–7 episodes/day Child: 20–30 mL/kg/day or 7–10 episodes/day
3	Maculopapular rash >50% BSA	6.1–15 mg/dL		Adult: >1500 mL/day or >7 episodes/day Child: >30 mL/kg/day or >10 episodes/day
4	Generalized erythroderma (>50% BSA) plus bullous formation and desquamation >5% BSA	>15 mg/dL		Severe abdominal pain with or without ileus or grossly bloody stool (regardless of stool volume).

Overall clinical grade (based on most severe target organ involvement):

Grade 0: No stage 1–4 of any organ.

Grade I: Stage 1–2 skin without liver, upper GI, or lower GI involvement.

Grade II: Stage 3 rash and/or stage 1 liver and/or stage 1 upper GI and/or stage 1 lower GI.

Grade III: Stage 2–3 liver and/or stage 2–3 lower GI, with stage 0–3 skin and/or stage 0–1 upper GI.

Grade IV: Stage 4 skin, liver, or lower GI involvement, with stage 0–1 upper GI.

**APPENDIX D: GRADING OF CHRONIC GVHD (NIH CRITERIA), (JAGASIA,
GREINIX ET AL. 2015)**

	SCORE 0	SCORE 1	SCORE 2	SCORE 3
PERFORMANCE SCORE: KPS ECOG LPS	 Asymptomatic and fully active (ECOG 0; KPS or LPS 100%)	 Symptomatic, fully ambulatory, restricted only in physically strenuous activity (ECOG 1, KPS or LPS 80-90%)	 Symptomatic, ambulatory, capable of self-care, >50% of waking hours out of bed (ECOG 2, KPS or LPS 60-70%)	 Symptomatic, limited self-care, >50% of waking hours in bed (ECOG 3-4, KPS or LPS <60%)
SKIN†				
SCORE % BSA GVHD features to be scored by BSA:	 No BSA involved	 1-18% BSA	 19-50% BSA	 >50% BSA

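### Once triggered, the mandatory ruxolitinib bilirubin row (Table 2-1) sets a recovery target below the entry value of many eligible participants with liver GVHD, and it conflicts with the resumption and discontinuation text

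*Combined protocol and SAP*

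**What the plan says.** Section 2.5.2.5, Table 2-1, has three bands for total bilirubin:

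- Lower Grade 3: "Grade 3: (> 3.0 – 5.0 x ULN): Decrease 1 dose level until resolved to" 3.0 x ULN or below.
- Upper Grade 3: "Grade 3: (>5.0 – 10.0 x ULN): Hold dose", again until 3.0 x ULN or below.
- Grade 4: hold until 3.0 x ULN or below. "If resolved in > 14 days, then drug must be discontinued". The numeric Grade 4 limit is not printed; above 10 x ULN is inferred from the top of the Grade 3 band.

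Footnote 2 makes every action mandatory unless footnoted otherwise, and the bilirubin row carries no such footnote. Baseline appears in the row once, and only for the length of monitoring: "LFTs should be monitored at least weekly until total bilirubin has resolved to baseline or stabilized over 4 weeks".

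Section 2.4 sets no bilirubin limit. Appendix C makes liver disease alone a route to eligibility: "Grade III: Stage 2–3 liver and/or stage 2–3 lower GI". Liver stage 4 gives Grade IV.

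Three further passages bear on the row. The opening of Section 2.5.2.5 limits dose changes to adverse events suspected of being caused by the drug. The text after Table 2-2 lets a reduced dose return to its previous level when parameters meet the eligibility thresholds. Section 2.5.2.6 requires discontinuation when an event attributed to ruxolitinib has not reached Grade 2 or better within 14 days of holding.

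**The concern.** Bilirubin is both the liver toxicity marker for ruxolitinib and the variable that stages liver GVHD. A recovery target in fixed multiples of ULN works when participants enter near normal. Here many can enter above it because of the disease that made them eligible. If such a participant has a rise suspected to come from ruxolitinib, falling all the way back to the entry value still leaves the row unsatisfied. A site following it exactly would keep the dose reduced or held, or in the Grade 4 band stop the drug, after the suspected drug effect had gone.

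The row belongs to the comparator only. T-Guard has no bilirubin row, and its general rule covers "Participants with another non-hematologic grade 3 or higher toxicity which is not attributable to an expected post-transplant event", with holding left to the physician. Under Section 5.5, stopping study drug is not itself a CR failure, but new systemic aGVHD therapy is. An avoidable interruption of ruxolitinib could therefore reach the primary endpoint through rescue or lost response.

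**Working it through.** The plan states no figure on this point, so there is none to reproduce. The check converts liver stages to multiples of ULN, then sets the passages side by side.

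**Inputs.** Appendix C: stage 1 is 2–3 mg/dL, stage 2 is 3.1–6, stage 3 is 6.1–15, stage 4 is above 15. Table 2-1: cut-offs at 3.0, 5.0 and 10.0 x ULN. ULN is not in the documents; 1.0 to 1.5 mg/dL is assumed.

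**Entry value against the recovery target.** Multiple = stage limit / ULN. Share of the stage 2 range above target = (6 − 3 x ULN) / (6 − 3.1), capped at 1.

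| ULN (mg/dL) | 3 x ULN (mg/dL) | Stage 2 (x ULN) | Stage 2 range above target | Stage 3 (x ULN) | Stage 4 (x ULN) |
|---|---|---|---|---|---|
| 1.0 | 3.0 | 3.1–6.0 | 100% | 6.1–15.0 | >15.0 |
| 1.1 | 3.3 | 2.8–5.5 | 2.7/2.9 = 93% | 5.5–13.6 | >13.6 |
| 1.2 | 3.6 | 2.6–5.0 | 2.4/2.9 = 83% | 5.1–12.5 | >12.5 |
| 1.3 | 3.9 | 2.4–4.6 | 2.1/2.9 = 72% | 4.7–11.5 | >11.5 |
| 1.5 | 4.5 | 2.1–4.0 | 1.5/2.9 = 52% | 4.1–10.0 | >10.0 |

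The percentages are shares of the mg/dL range, not of patients. Stage 1 is at most 3.0/1.0 = 3.0 x ULN and never exceeds the target. All of stage 2 exceeds it only if ULN is below 3.1/3 = 1.03. All of stage 3 exceeds it if ULN is below 6.1/3 = 2.03.

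**Example.** Entry at 8 mg/dL is 8/1.5 = 5.3 to 8/1.0 = 8.0 x ULN, inside the hold band throughout. After a suspected drug-related rise and return to 8, the row still requires a hold. Its target is 3.0 to 4.5 mg/dL, which is (8 − 4.5)/8 = 44% to (8 − 3.0)/8 = 63% below entry.

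**Passages side by side.**

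- *Re-escalation text after Table 2-2.* It refers to eligibility thresholds. None exists for bilirubin, so the text cannot be applied to this parameter.
- *Section 2.5.2.6.* An attributed event not at Grade 2 or better within 14 days of holding, or a Grade 3 abnormality lasting more than 14 days, leads to discontinuation. For recovery after more than 14 days, the row keeps the reduced dose (>3.0–5.0 x ULN) or restarts one level lower (>5.0–10.0 x ULN). For the same slow recovery, one passage stops the drug and the other continues it.
- *Neighbouring rows.* Creatinine at Grade 2 accepts "Grade 1 or baseline, then resume initial dose level". ALT/AST has baseline-dependent rules at Grades 2 and 4, but its Grade 3 bands, like creatinine at Grade 3, are not referenced to baseline.

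**How many.** Table 1-3 reports raised bilirubin of Grade 3 or higher by Day 28 in 3 of 152 ruxolitinib patients. 3/152 x 123 = 2.4. If all three fell among the 101 Grade III–IV ruxolitinib patients cited in Section 5.1.5, 3/101 x 123 = 3.7. That gives about 2 to 4 of 123. At the planned 26% CR rate, losing every CR among 4 participants costs 4 x 0.26 = 1.0 CR, or 1/123 = 0.8 percentage points.

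**The case against.** The strongest reply is attribution. A reader might infer that ruxolitinib must be reduced, held or stopped because of liver GVHD itself. The documents do not support that: the opening of Section 2.5.2.5, the table title and Section 2.5.2.6 all limit action to events suspected of, or attributed to, ruxolitinib. Section 4.4.3 has investigators weigh the underlying indication, and Section 4.4.4 keeps GVHD out of AE reporting. This stands, and it confines the problem to raised-baseline participants whose later rise is suspected to be drug related. It does not remove the problem, because attribution governs entry to the row, not exit from it. Suspicion is also a low bar where drug effect and active liver GVHD look alike.

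A reader might also infer a material bias toward T-Guard. Day 28 CR needs liver stage 0, that is, bilirubin below 2 mg/dL, so a participant still above 3.0 x ULN from liver GVHD on that day is a non-CR whatever the dosing rule. No document shows that bilirubin-driven holds change CR. Separate rules for four infusions and for continued oral dosing are not in themselves a defect. These points stand.

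Two smaller points also stand. The neighbouring rows refer to baseline only in part, so the comparison with them is supporting evidence only. Footnote 1 points to CTCAE v5, which is not in the documents, so whether its grading allows for an abnormal baseline cannot be settled here; the row's printed targets make no such allowance.

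**Conclusion.** The point holds in a limited form. A mandatory row does not fit part of the eligible population: for entry values above 3.0 x ULN, once the row is triggered, return to baseline is not recovery. It also cannot be applied together with the re-escalation text and Section 2.5.2.6 as written. The mandatory stop within the row is in the Grade 4 band only; its Grade 3 bands lead to reduction or holding.

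Not every liver-involved participant is exposed: stage 1 and, at ULN of 1.04 or more, part of stage 2 lie at or below the target. The Phase 1/2 study had "18 with GI (90%) and 5 with liver (25%) involvement", and 25% of 123 is about 31 ruxolitinib participants with any liver stage. A reader might take that as the number affected, but the stage split is not given and a raised baseline alone triggers nothing. The better guide is about 2 to 4 of 123, with at most about 0.8 percentage points of control-arm CR at stake. That count assumes that the Table 1-3 rate carries over. Its events are not limited to drug-attributed ones or to participants with raised baselines, and reporting may differ here. The ULN range is also an assumption. The case for change rests on a rule sites cannot apply consistently, not on a distorted primary comparison.

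**What to change.** In the next amendment, reconcile the bilirubin row with the attribution condition in Section 2.5.2.5, the re-escalation text after Table 2-2, Section 2.5.2.6, Appendix C and the eligibility criteria. The row should state which reference applies when bilirubin at randomization already exceeds a trigger or the recovery value, and how values attributed to liver GVHD are handled. It should also be clear which passage governs Grade 3 recovery that takes more than 14 days. The sponsor's safety and pharmacology leads choose the values; none is proposed here. Record the attributed cause, drug or liver GVHD, of each bilirubin-driven hold or stop, so that the effect on comparator exposure can be described.

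The cost is one table row, matching cross-references and one data item. No new tests are needed, because bilirubin is already part of every aGVHD evaluation.

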2.5.2.6 Ruxolitinib Discontinuation

Ruxolitinib must be discontinued upon any one of the following AE attributed to ruxolitinib that fails to resolve to a Grade 2 or better within 14 days of holding drug, or if a lower re-start dose or administration schedule subsequent to any of the following non-hematologic toxicities is either not available or likely to be clinically ineffective:

- Occurrence of a Grade 4 laboratory or non-laboratory abnormality attributable to ruxolitinib
- Occurrence of a Grade 3 laboratory or non-laboratory abnormality attributable to ruxolitinib that remains at Grade 3 or worse for greater than 14 days
- Withdrawal of consent by the participant
- General or specific changes in the participant's condition render the participant unacceptable for further treatment in the opinion of the investigator

2.5.2.7 Corticosteroid Dosing

Participants must be on 2 mg/kg/day of methylprednisolone (or corticosteroid equivalent) at enrollment and continue through the start of ruxolitinib or T-Guard therapy. For participants with SR-aGVHD a gradual taper of steroids rather than an abrupt discontinuation of steroids is recommended. Corticosteroid taper may be done per institutional practice or may follow a 10% dose reduction every 5 days in participants demonstrating CR/PR as observed by the Investigator, beginning no earlier than Day 7 and continuing to approximately Day 56 to allow 7-8 week taper. Each dosing change of corticosteroids must be reported.

2.5.2.8 Calcineurin Inhibitor (CNI) Tapering

Tapering of immunosuppression in responding patients will follow 2 steps:

1. Taper of corticosteroids (see above),
2. Followed by taper of calcineurin inhibitor (CNI)

CNI (cyclosporine or tacrolimus) tapering will follow a 25% dose reduction per month starting from Day 56 in patients demonstrating complete resolution of all signs/symptoms of aGVHD, once off systemic corticosteroids.

2.5.3 Supportive Care

2.5.3.1 GVHD Prophylaxis Medications

Medications such as cyclosporine, tacrolimus, methotrexate (MTX), mycophenolate mofetil (MMF) may be continued, resumed, or increased to therapeutic doses per provider discretion, and adjusted/discontinued as necessary for renal, central nervous system (CNS) or other toxicity using institutional management guidelines. Close monitoring of drug levels is strongly recommended. Resumption of a GVHD prophylaxis agent is not considered the addition of a second agent.

Overall start and stop dates of immunosuppressants will be captured for this study. However, for agents where dosing is tapered in response to drug levels, the medication dosing will not require reporting.

2.5.3.2 Topical and Ancillary GVHD Therapies

Topical treatment for aGVHD is allowed and should be used according to institutional practices. Topical treatment, including corticosteroid creams, topical tacrolimus, oral beclomethasone or budesonide, topical azathioprine and ophthalmic glucocorticoids, is not considered as secondary systemic treatment.

Ancillary/supportive care measures for aGVHD such as the use of anti-motility agents for diarrhea, including octreotide, is allowed at the discretion of the treating physician. Use of ursodiol to prevent/reduce gall bladder sludging or prevent transplant-related hepatic toxicity is also allowed according to institutional guidelines.

2.5.3.3 Other Supportive Care Guidelines

In addition to study treatment, all participants should receive the following per institutional practice:

- Transfusion support
- Anti-infective prophylaxis against herpes viruses, *Pneumocystis jiroveci*, bacterial and fungal infections.
- Routine CMV antigenemia/viral load testing by hybrid capture or PCR based methods (with preemptive treatment in participants who develop a positive assay). CMV testing is required weekly through at least Day +56 post randomization. Prophylaxis against CMV is allowed. Any CMV disease requiring treatment will be captured on an Infection Form.

- In addition to the required monitoring for EBV according to the study calendar, monitoring for viral infections such as EBV, adenovirus, and HHV6 is encouraged for participants at high risk in accordance with institutional practice. Participants with rapidly rising EBV DNA levels or clinical symptoms are recommended to have imaging studies to diagnose an EBV PTLD. EBV PTLD may rapidly progress and can be fatal if not treated. Management of suspected EBV PTLD should be discussed with one of the Protocol Chairpersons. EBV PTLD can be treated with rituximab and/or infusion of 106 T-cells/kg from the donor. It is recommended that participants with EBV DNA levels of > 1000 copies/mL receive 375 mg/m² of rituximab. Those participants that continue to have levels above 1000 copies/mL on subsequent testing should be considered to receive three additional weekly infusions of 375 mg/m² of rituximab. An accelerated schedule of days 1, 4, 8, 15 can be used if there is a suspicion of EBV PTLD. Rituximab has been shown to induce regression in 50 - 70% of cases. Note: Rituximab does not enter the CNS and is not effective in treating CNS disease. Donor lymphocyte infusions may induce regression in > 90% of cases of EBV PTLD and are effective in CNS disease.
- Co-enrollment onto supportive care and infectious disease protocols will be allowed on case-by-case basis and requires approval by study chair or officer and sponsor.

2.5.3.4 Salvage Treatment Guidelines

Addition of any new systemic immunosuppressive therapy by the Investigator after the start of T-Guard or ruxolitinib treatment is allowed:

- After 7 days for participants meeting aGvHD criteria for progression or mixed response
- After 14 days for participants meeting aGVHD criteria for no response

In case T-Guard infusions are delayed (e.g., for toxicity reasons) the day 7 and 14 timepoints will shift accordingly.

Requirement for initiation of new systemic immunosuppressive therapy will be considered a treatment failure. In this case, the participant must discontinue study treatment.

